**Attachment E**

**Anticoagulation Protocol**

### Anticoagulation Protocol

The anticoagulation strategies recommended in the 2012 HRS/EHRA/ECAS expert consensus statement on catheter and surgical ablation for atrial fibrillation should be followed to manage the anticoagulation therapy for subjects enrolled in both arms of the study.

#### Pre-procedure

- Systemic anticoagulation at a therapeutic level should be maintained 3 to 4 weeks prior to the procedure.
- A TEE or ICE evaluation should be performed prior to the ablation procedure, to evaluate for the presence or absence of left atrial thrombus.
- The presence of a left atrial thrombus is an intra-op study exclusion.

#### During the procedure

- An ACT of 300 to 400 secs should be maintained during the endocardial catheter ablation procedure.
- Administration of protamine following ablation to reverse heparin should be considered.

#### Post-procedure

- Systemic anticoagulation therapy should be initiated for all patients post procedure through at least two months following the ablation procedure.
- Decisions regarding the use of systemic anticoagulation more than two months following ablation should be based on the patient's risk factors for stroke and not on the presence or type of AF.
- Discontinuation of systemic anticoagulation therapy post ablation is generally not recommended in patients who are at high risk of stroke as estimated by currently recommended schemes (CHADS2 or CHA2DS2VASC).

**Attachment F**

**Repeat Catheter Ablation Protocol**

**Repeat Catheter Ablation Protocol**

In the event that an AF/AFL/AT reoccurs post procedure for a subject in either the treatment arm or control arm of the study and a repeat catheter ablation procedure is performed, various diagnostics should be performed to evaluate reasons for failure of the index procedure.

Voltage mapping to be performed to determine and document the breakthrough locations and extents

**Interrogate and Complete Pulmonary Vein Isolation**

- Pulmonary vein isolation should be determined for each vein and documented as to whether they remained isolated or did they reconnect.
- The location and extent of breakthroughs to the reconnected pulmonary veins should be determined for each vein and documented.

**Interrogate Reoccurred Posterior Electrical Activity**

- The posterior left atrium should be evaluated with respect to electrical activity. Voltage mapping should be performed to document the degree of electrical silencing along the posterior left atrium.

**Document Ablation Locations**

- All endocardial ablation locations should be documented; 3-D navigation tools help to identify and document the locations and extents of endocardial ablation.

PV	Pulmonary vein
QoL	Quality of life
SAE	Serious adverse event
SOC	System organ class
TEAE	Treatment-emergent adverse event
TEE	Trans-esophageal echocardiogram
TIA	Transient ischemic attack
TTE	Trans-thoracic echocardiogram

1 INTRODUCTION

This document describes the statistical methods and data presentations to be used in the summary and analysis of CONVERGE Protocol VAL-1200(E). Background information is provided for the overall study design and objectives. The reader is referred to the study protocol and electronic case report forms (eCRFs) for details of study conduct and data collection.

2 STUDY OBJECTIVES, TREATMENTS, AND ENDPOINTS

2.1 Study Objectives

The objectives of this randomized, open-label pivotal study are to evaluate the safety and efficacy of the EPi-Sense®-AF Guided Coagulation System with VisiTrax® (referred to in this document as EPi-Sense-AF procedure or convergent procedure) for the treatment of symptomatic persistent atrial fibrillation (AF) subjects who are refractory or intolerant to at least one Class I and/or III anti-arrhythmic drug (AAD) as compared to a standalone endocardial catheter ablation.

2.1.1 Primary Efficacy Objective

The primary objective is to demonstrate superiority of the experimental convergent procedure (EPi-Sense-AF) compared to the stand-alone endocardial catheter ablation (control) on overall success, defined as freedom from AF/AFL/AT (atrial fibrillation/atrial flutter/atrial tachycardia) absent Class I or III anti-arrhythmic drugs (AADs), except for previously failed Class I or III AADs with no increase in dosage, following the 3 month blanking period through the 12 months post-procedure follow-up visit.

2.1.2 Primary Safety Objective

The incidence rate of major adverse events (MAEs) in the treatment arm will be documented to demonstrate an acceptable risk profile.

2.1.3 Secondary Objectives

The secondary objectives are to demonstrate the efficacy of EPi-Sense-AF as:

- A 90% reduction in the subject's baseline AF burden (percent of time a subject is in AF) at 12 months post-procedure in the presence or absence of Class I/III AADs.
- Change in QoL measures from baseline to 12 months post-procedure.
- Change in six minute walk test scores from baseline to 12 months post-procedure.

2.1.4 Exploratory Objectives

The exploratory objectives are to:

- Demonstrate the efficacy of EPi-Sense-AF procedure as a 90% reduction in the subject's baseline AF burden at 18 months post-procedure, in the presence or absence of Class I/III AADs.
- Explore the impact of the EPi-Sense-AF convergent procedure on left atrial size.
- Explore the impact of the EPi-Sense-AF convergent procedure on left ventricular ejection fraction (LVEF).

In addition, the following may be evaluated for a health economics data analysis:

- Number of hospitalizations.
- Total number of days hospitalized.
- Number of rhythm disturbance treatments for a period of 12 months before and 6 to 18 months after the convergent procedure.

In addition, the following clinically relevant assessment for non-paroxysmal subjects from 2017 Heart Rhythm Society (HRS) guidelines will be evaluated, data permitting:

- Freedom from AF/AFL/AT requiring intervention (emergency visits, cardioversion, urgent care visit, re-ablation, etc.).
- Significant reduction in AF burden: 75% reduction from pre- to post-ablation, evaluated at 6 and 12 months.
- Total post-ablation burden of 12%, evaluated at 6 and 12 months.
- Freedom from stroke-relevant AF/ AFL/AT-duration (cutoff of 1 hour).
- Regression of AF: conversion of persistent to paroxysmal AF.
- Prevention in AF progression: time to first episode of persistent AF.

2.2 Treatment Arm Comparisons

The EPi-Sense-AF Guided Coagulation System with VisiTrax will be compared to a standalone endocardial catheter ablation for the treatment of symptomatic persistent AF in subjects who are refractory or intolerant to at least one Class I and/or III AAD.

The test procedure is the minimally invasive “EPi-Sense-AF” procedure using the device, EPi-Sense-AF Guided Coagulation System with VisiTrax combined with an open irrigated radiofrequency ablation catheter to complete pulmonary vein isolation by ablating breakthroughs between the epicardial lesions. The EPi-Sense-AF is able to coagulate cardiac tissue from the epicardial surface, allowing the procedure to be performed on a beating heart, endoscopically without chest incisions, lung deflation, or dissections of the pericardial reflections (attachments between the pericardium and atrium).

The reference or control procedure is standard standalone endocardial “catheter ablation” described in Attachment B of the protocol.

2.3 Study Endpoints

2.3.1 Primary Efficacy Endpoints

The primary efficacy endpoint is success or failure to be AF/AT/AFL free absent class I and III AADs except for a previously failed or intolerant class I or III AAD with no increase in dosage following the 3 month blanking period through the 12 months post procedure follow-up visit.

Subjects will be considered primary efficacy failures if any of the following conditions are observed:

- Any electrocardiographically documented AF/AFL/AT episode of 30 sec duration or longer by Holter, event monitor or rhythm strip; or for the full 10 second recording of a standard 12 lead ECG following the 3 month blanking period through the 12 months post procedure follow-up visit.
- The use of a new or an increase in the dose of a previously failed class I or class III AAD following the 3 month blanking period through the 12 months post procedure follow-up visit.
- DC cardioversion for AF/AFL/AT following the 3 month blanking period through the 12 months post procedure follow-up visit.
- Subsequent left-sided catheter ablation for AF/AFL/AT at anytime during the 12 months post procedure follow-up visit.
- Catheter ablation for right-sided typical atrial flutter following the 3 month blanking period through the 12 months post procedure follow-up visit.

As described in Section 7.4.2, the blanking period is the period from index procedure through 3 months post-procedure visit.

2.3.2 Secondary Efficacy Endpoints

The secondary efficacy endpoints are:

- Success or failure to achieve a 90% reduction from baseline AF burden and off all Class I and III AADs at 12 months post-procedure.
- Success or failure to achieve a 90% reduction from baseline AF burden regardless of their Class I and III AAD status at 12 months post-procedure.
- Change in SF36 Quality of Life (QoL) scale scores and composite scores from baseline values to 12 months post-procedure.
- Change in University of Toronto Atrial Fibrillation Symptom Scale (AFSS) composite score from baseline values to 12 months post-procedure.
- Change in distance walked during the 6 minute walk test from baseline values to 12 months post-procedure.
- Success or failure to be AF free and off all Class I and III AADs except for a previously failed or intolerant Class I or III AAD with no increase in dosage following the 3 month blanking period through the 12 months post-procedure follow-up visit.
- Success or failure to be AF free, regardless of Class I and III AAD status following the 3 month blanking period through the 12 months post-procedure follow-up visit.

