6.5 Significance Level

Unless otherwise noted, all statistical analyses will be conducted with a significance level (α) of 0.05 and utilize two-sided testing.

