9.2 Multiplicity Adjustment

The fixed-sequence procedure[1,2] will be used to evaluate the following secondary endpoints. Each of these tests will be tested at the same significance level ($\alpha=0.05$) in this predetermined order. Each endpoint is only tested if the prior endpoint is successful ($p \leq 0.05$). This procedure does not inflate the Type I error rate since the sequence is prospectively specified and no further testing is performed once an endpoint in the sequence fails to show significance ($p > 0.05$)[2]. All tests will be performed on the ITT population. If sufficient data have not been collected during this study to permit the evaluation of a given endpoint, that endpoint should be skipped and the subsequent endpoint evaluated:

- 1) Achievement of $\geq 90\%$ reduction in baseline AF burden at 12 months post-procedure, where subjects with new or increased dosage of Class I/III AADs during the efficacy evaluation period are categorized as not achieving $\geq 90\%$ reduction, using the Fisher's Exact test as described in Section 9.4.1.

- 2) AF freedom during efficacy evaluation period, using the chi-square or Fisher's Exact test as described in Sections 9.4.5 and 9.1, where subjects with new or increased dosage of Class I/III AADs during the efficacy evaluation period are categorized as not achieving AF freedom.
- 3) Achievement of $\geq 90\%$ reduction in baseline AF burden at 12 months post-procedure, regardless of Class I/III AAD usage, using the Fisher's Exact test as described in Section 9.4.1.
- 4) AF freedom during efficacy evaluation period, using the chi-square or Fisher's Exact test as described in Sections 9.4.5 and 9.1, regardless of Class I/III AAD usage.
- 5) Change in AFSS composite score at 12 months post-procedure, using an ANCOVA model as described in Section 9.4.3.
- 6) Change in SF-36 physical health composite score at 12 months post-procedure, using an ANCOVA model as described in Section 9.4.2.
- 7) Change in SF-36 mental health composite score at 12 months post-procedure, using an ANCOVA model as described in Section 9.4.2.
- 8) Change in distance walked during six-minute walk test at 12 months post-procedure, using an ANCOVA model as described in Section 9.4.4.
- 9) Change in left ventricular ejection fraction (LVEF) at 6 months post-procedure, as described in Section 9.5.2.
- 10) Atrial remodeling assessed by a decrease in left atrial size at 6 months post-procedure, as described in Section 9.5.3.

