9.4.2 SF-36

The SF-36^[4,5] is administered at the Baseline and 12 month visits. The SF-36 collects items across the physical functioning, role-physical, bodily pain, general health, vitality, social functioning, role-emotional, and mental health scales. Those scales are then combined into 2 overall summary measures, for physical health and mental health. Item scores are summed (after reverse coding the 10 items requiring it) to form the raw scale scores, which are rescaled to a 0-100 scale and standardized using a z-score transformation based on SF-36 scale means and standard deviations from the general U.S. population, as provided in the scoring manual^[2,3]. Aggregate scores for the physical and mental health components are then calculated using weighted averages of the standardized scale scores, and standardized into the physical and mental health component scores using a T-score transformation to have a mean of 50 and a standard deviation of 10. Lower scores reflect poorer quality of life.

The algorithm from scoring manual^[2,3] is provided as follows for ease of reference but [2,3] remains the definitive reference.

The raw scale scores are calculated as follows, where missing values (as long as <50% of item scores are missing) are imputed as the mean score of the other item scores, after any recoding of those scores has been performed:

- **Physical Functioning:** #3a, 3b, 3c, 3d, 3e, 3f, 3g, 3h, 3i, 3j – sum of scores, where ≥ 5 item scores are non-missing.
- **Role-Physical:** #4a, 4b, 4c, 4d – sum of scores, where ≥ 2 item scores are non-missing.
- **Bodily Pain:** #7, 8 – sum of scores, where at least 1 item score is non-missing:
 - #7 recoded, 1 \rightarrow 6.0, 2 \rightarrow 5.4, 3 \rightarrow 4.2, 4 \rightarrow 3.1, 5 \rightarrow 2.2, 6 \rightarrow 1.0
 - #8 recoded, based on item score and original (pre-coded) score for

item #7: if score for #7 and #8 are both 1, recode #8 to 6; if score for #7 is 2 – 6 and score for #8 is 1, recode #8 to 5; if score for #8 is 2 – 5 and item #7 is non-missing, recode #8 to (6-score). If item #7 is missing, recode #8 to: 1 → 6.0, 2 → 4.75, 3 → 3.5, 4 → 2.25, 5 → 1.0.

- **General Health:** #1, 11a, 11b, 11c, 11d – sum of scores, where ≥ 3 item scores are non-missing.
 - #1 recoded, 1 → 5.0, 2 → 4.4, 3 → 3.4, 4 → 2.0, 5 → 1.0.
 - #11a and #11c: not recoded.
 - #11b and #11d: recoded as 6 – score.
- **Vitality:** #9a, 9e, 9g, 9i – sum of scores, where ≥ 2 item scores are non-missing.

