- Physical health component score (PCS) = $50 + AGG_PHYS*10$
- Mental health component score (MCS) = $50 + AGG_MENT*10$

The transformed scale scores (on a 0-100 scale) and norm-based component scores, and their changes from baseline, will be summarized by time point and treatment arm. Raw item scores, as well as transformed scale scores and norm-based component scores will be listed by subject.

The changes from baseline at 12 months will be analyzed using an analysis of covariance (ANCOVA) model with the scale or component score as the dependent variable, and treatment arm and baseline scale or component score as covariates.

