9.4.3 Atrial Fibrillation Severity Scale (AFSS)

The University of Toronto's AF Severity Scale is also administered at the Baseline and 12 month visits. An overall subject-perceived severity score will be created by taking the mean of the results from item #7 (severity of most recent episode of irregular heart rhythm) and item #8 (severity of first episode of irregular heart rhythm), both scored as 1 = not at all severe and 10 = extremely severe. A composite score for total AF burden will be calculated by adding overall severity score to the result from item #5 (average frequency of AF, scored from 1=continuous to 11=less than once a year) and the result from item #6 (average duration of AF, scored from 1=continuous to 8=a few minutes), resulting in a range of possible scores from 3 – 29.

This calculation was described previously^[6] although Dorian et al erroneously stated the possible score range as 3-30. If any of the item results making up either the subject-perceived severity score or the composite score is missing, that score will also be missing.

Individual item results, as well as the composite score, will be listed by subject and time point. The results for items #4 (global well-being, scored 1-10), #5 (AF frequency), and #6 (AF duration), as well as the overall severity score and composite score will be summarized by time point and treatment arm, as will their change from baseline.

The changes from baseline at 12 months will be analyzed separately for each of those five scores using an ANCOVA model with the score as the dependent variable, and treatment arm and baseline score as covariates.

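### The eight SF-36 scale scores are named secondary endpoints and tested at two-sided 0.05, but they lie outside the fixed sequence and nothing labels them supportive

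*SAP*

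**What the plan says.** SAP 2.3.2 includes among the secondary efficacy endpoints "Change in SF36 Quality of Life (QoL) scale scores and composite scores from baseline values to 12 months post-procedure". The next entry in that list, for the University of Toronto AF scale (AFSS), names only its composite score. The SAP thus distinguishes scales from composites, and for the SF-36 it gives both secondary status.

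SAP 9.4.2 identifies eight scales: "The SF-36 collects items across the physical functioning, role-physical, bodily pain, general health, vitality, social functioning, role-emotional, and mental health scales". These are combined into a physical (PCS) and a mental (MCS) component score. On analysis it says: "The changes from baseline at 12 months will be analyzed using an analysis of covariance (ANCOVA) model with the scale or component score". That score is the outcome; its baseline value and the arm are the covariates. The section sets no condition on earlier results. SAP 6.5 supplies the level: unless noted otherwise, "all statistical analyses will be conducted with a significance level (α) of 0.05 and utilize two-sided testing".

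SAP 6.4 refers multiplicity to SAP 9.2 and nowhere else. SAP 9.2 is a 19-step fixed sequence that stops at the first non-significant step. Its only SF-36 entries are test 6, "Change in SF-36 physical health composite score at 12 months post-procedure, using an ANCOVA model as described in Section 9.4.2", and test 7, the matching mental composite.

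For the AFSS, SAP 9.4.3 says: "The changes from baseline at 12 months will be analyzed separately for each of those five scores using an ANCOVA model". One of the five is the composite, which is test 5.

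**The concern.** The sequence exists to protect the conclusions drawn from endpoints other than the primary. Every other entry in SAP 2.3.2 has a counterpart among tests 1 to 8. Tests 9 to 19 are all items that SAP 2.3.5 calls exploratory, such as LVEF, left atrial size and hospitalizations. The plan therefore gates eleven exploratory tests and leaves eight named secondary endpoints ungated.

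Stopping the sequence does not stop the scale tests. Suppose test 1 fails. PCS and MCS are then no longer eligible under SAP 9.2, yet eight scale p-values for named secondary endpoints are still produced, because SAP 15.1.1 lists an analysis table that covers both component and scale scores. Nothing in the SAP tells a reader of that table that a scale result below 0.05 carries less weight than a composite that passed the sequence.

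The data are meant to support a premarket application (Protocol 1.1). The trial is open label, and the SF-36 is reported by the patient. An isolated significant scale is the kind of result that gets presented as a met secondary endpoint unless the plan says otherwise.

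**Working it through.** **Plan's own figure.** The documents state no family-wise error rate for the scales and no correlation among them, so there is nothing to reproduce. The inputs are:

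- number of scales, m = 8 (SAP 9.4.2);
- level per test, α = 0.05 two-sided, which is 0.025 in each direction (SAP 6.5);
- adjustment across the eight: none (SAP 6.4 and 9.2);
- common correlation ρ of the eight test statistics: **assumed**, from 0 to 0.9.

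**Independent tests, no true difference on any scale.**

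- Either direction: 1 − (1 − 0.05)^8 = 1 − 0.95^8 = 0.337.
- Favouring convergent only: 1 − (1 − 0.025)^8 = 1 − 0.975^8 = 0.183.

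**Correlated tests.** Take each statistic as standard normal, Z_i = √ρ·T + √(1−ρ)·e_i, with T shared and the e_i independent. With c = 1.96,

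P(at least one |Z_i| > c) = 1 − ∫ φ(t) · [Φ((c − √ρ·t)/√(1−ρ)) − Φ((−c − √ρ·t)/√(1−ρ))]^8 dt.

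For results in one direction only, drop the second Φ term. Numerical integration gives:

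| Assumed ρ | Any p ≤ 0.05 | Any p ≤ 0.05 favouring convergent |
|---|---|---|
| 0 | 33.7% | 18.3% |
| 0.3 | 30.0% | 15.2% |
| 0.5 | 25.0% | 12.5% |
| 0.7 | 19.1% | 9.5% |
| 0.9 | 11.9% | 6.0% |
| One test, for reference | 5% | 2.5% |

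Even at ρ = 0.9 the rate is 2.4 times that of a single test, on either count (11.9/5 and 6.0/2.5). The expected number of false positives does not depend on ρ: 8 × 0.05 = 0.4 in total, or 8 × 0.025 = 0.2 favouring convergent.

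**Does any text remove the scales from the claim family?**

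- SAP 2.3.2 gives them secondary status without qualification.
- SAP 9.4.2 gives them the same model as the composites and no descriptive, nominal or supportive label.
- SAP 6.5 allows exceptions to the 0.05 level, but none is stated for the scales.
- The stopping rule in SAP 9.2 speaks of endpoints in the sequence, and the scales are not in it.
- Protocol 1.5.2 lists only change in QOL measures, and Protocol 9.5 has no multiplicity rule, so the Protocol does not settle the matter.

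**The case against.** The strongest reply is that SAP 9.4 says how each variable is analysed, while SAP 9.2 says which results carry inferential weight. SAP 9.4.2 also fits the PCS and MCS models unconditionally. If an unconditional analysis licensed a claim, every endpoint would bypass the sequence and SAP 9.2 would be pointless. The output list fits this view: the sequential tests have their own table (14.2.1.7), while the scales appear in a separate one (14.2.4.1). SAP 9.1 states when a significant difference will be concluded for the primary endpoint, and no such rule exists for a scale. On this reading the composites are already the SF-36 tests that count, and only a sentence is missing.

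Much of this stands. A reader might infer that the plan lets a single significant scale count as a met secondary endpoint with a 25% family-wise error rate. The documents do not support that, for three reasons:

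- No text says what a significant scale would be taken to show.
- The 25% requires a correlation of 0.5, which the documents do not give.
- It counts results in either direction, whereas a benefit claim concerns one direction, where the rate is half as large.

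A reader might also add the four other AFSS scores and quote a rate for twelve tests. SAP 2.3.2 names only the AFSS composite as secondary, so that rate would mix named endpoints with scores that were never endpoints.

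The reply does not explain why SAP 2.3.2 gives the scales the same status as the composites. The division of labour between 9.2 and 9.4 has to be inferred, and for eight named secondary endpoints it should be written down.

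**Conclusion.** The structural gap is real. Eight named secondary endpoints are tested at two-sided 0.05, lie outside the only multiplicity control, and are neither labelled supportive nor made conditional on the sequence. What SAP 9.2 says about not inflating Type I error does not extend to them.

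For the eight scales together, the chance of a false positive in either direction runs from 34% (independent) through 25% (correlation 0.5) to 12% (correlation 0.9). For a false finding in favour of the convergent procedure it is 18%, 12.5% and 6%. These figures assume no true difference on any scale, a common correlation, and normal test statistics. If some scales truly differ, fewer null tests remain and the rate falls.

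The documents neither promise nor forbid a claim on a scale, so this is exposure left by silence, not a planned overclaim. The error rates of the primary endpoint and of the listed sequence are unchanged. It is a cheap improvement: small to make, but it settles what the trial may conclude about quality of life.

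**What to change.** In SAP 2.3.2, keep the PCS and MCS as the SF-36 secondary endpoints, matching tests 6 and 7. In SAP 2.3.2 and 9.4.2, state that the eight scale scores are supportive: reported as estimated arm differences with 95% confidence intervals and nominal p-values, with no significance claim whatever the outcome of the sequence. For consistency, put the same label in SAP 9.4.3 on the four AFSS scores that are not the composite (well-being, frequency, duration and overall severity).

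The cost is a few sentences, best written before database lock. Data collection, sample size, primary analysis and the order of the sequence all stay as they are. The one real loss is that an isolated significant SF-36 scale can no longer be presented as a met secondary endpoint.
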